9.5 Data sources

9.5.1 Data obtained from users

Baseline and 6-weeks and 12-weeks data regarding sleep, stress, and mental health questionnaires including:

1	Regensburg Insomnia Scale
2	Schlaffragebogen B
3	Short Form 12 Health Survey Questionnaire (SF-12)
4	Pittsburgh Sleepiness Quality Index (PSQI)
5	Perceived Stress Scale (PSS)

9.5.2 Data imported from the Dein Schlaf. Dein Tag. App

Digital data objectively measured using the Dein Schlaf. Dein Tag. App will contain the following parameters,

- Sleep stage and sleep-wake data included by not limited to total sleep time, sleep onset latency, wake after sleep onset, sleep efficiency and usage patterns.

9.6 Study size

An a priori power analysis was performed using GPower version 3.1.9.7. Previous research indicates that effect sizes between 0.20 and 0.50 can be expected using a digital sleep application. A conservative approach (assuming an effect size of 0.20) will require 150 participants in each group (N=150) to detect significant effects between app group and wait-list control group for both primary and secondary outcome measures (alpha: 0.05, power: 0.80, allocation ratio 1:1). As trials with solely online recruitment may have higher drop out rates, we increased the participants in each group to 300 (total: 600 participants).

9.7 Data management

Applicable national and international legal requirements for data handling and data archiving will be met. Participant study materials including recruitment materials, participant informed consent documents (PICF), study withdrawal forms, and study progress will be collected using an EU data center of Forsta/Decipher which is GDPR compliant, ISO 27001 certified, with SOC2 accredited data centers.

Objective sleep data will be collected using the Dein Schlaf. Dein Tag. application, and stored within an EU data center of the Microsoft Azure cloud system, an ISO 27001 certified and SOC 1, SOC 2, and GDPR compliant cloud service provider. Self-reported questionnaire data will be captured using an EU data center of Forsta/Decipher which is GDPR compliant, ISO 27001 certified, with SOC2 accredited data centers. Objective sleep data is encrypted in transit and at rest and additionally, personally identifiable information is hashed before being stored in the database. Access to databases for data analysis which include person identifiable information is limited to approved administration staff and is locked to the corporate IP address in the EU.

Personal information identifiers are separated from measurements so that employees of SleepScore Labs International LTD can work with accordance of least privilege to perform adequate work duties. Authentication controls are also implemented to protect customer data using passwords and usernames – external parties do not have any authentication services. Upon completion of data collection, de-identified objective data from Microsoft Azure cloud system and self-reported Forsta/Decipher data will be merged into a GDPR compliant data repository. Azure Data Factory will be used to combine the data, with processed data being stored in a Microsoft Azure SQL Server hosted in the EU. Access to this repository, which is required for analysis, will be limited to specific EU-based employees.

9.7.1 Personal data and data protection

Data collected in the course of this study are subject to strict data protection measures. Objective data in the system is encrypted and secure while in transit and at rest using the latest security protocols. The data protection notice informs end-users about their data protection rights and how to exercise them (i.e. make data subject rights requests). We will comply with the requirements of Articles 12 to 21 GDPR, as applicable. All study participant data that is recorded will be pseudonymized for storage and analysis: Objective sleep data from the app as collected and controlled by SleepScore Labs and self-reported questionnaire data as collected by a vendor on behalf of ResMed Objective sleep data from the Dein Schlaf. Dein Tag. App as specified in this protocol, and without personal identifiers will be send to vendor, combined with self-reported questionnaire data by vendor and equipped with new identifiers to result in a de-identified set of study data. At the end of the project, the data will be deleted from the vendor's servers, transferred to ResMed and shared with Sleepscore Labs for joint analysis. De-identified study data will be stored at ResMed for 10 years.. Data will be collected and processed to reach the goals of the study and furthermore possible evaluations for sleep research and publications. Participants will be informed about their rights in terms of data usage, data storage, correction of data and deletion of stored data through the data protection notice. This notice sets out the data protection rights of the user and how they can exercise their data protection rights under GDPR.

9.8 Data analysis

Demographic and other key study variables will be compared between intervention group and control group at the baseline using t tests for continuous variables and chi squared for categorical variables to test whether the randomization has worked adequately.

The primary analysis will include all randomized participants. Secondary analyses will be conducted using an adherent to treatment approach, excluding participants who did not sufficiently engage with app throughout the study (<3 tracked nights of sleep per week, respectively used the app modules regularly).

The questionnaire data will be analyzed by an ANOVA, with one factor (app condition vs. waitlist control group) and time (Baseline, 6-weeks, 12-weeks). To handle missing values, a mixed-model approach with the same factors will be applied. The critical statistical test would be the interaction term between app condition and the waitlist control group.

For objectively recorded sleep data, repeated measured data will be analyzed using multi-level modeling (MLM) in a nested way (nights within participants), will be performed allowing for analyzing changes with the intervention (app) group. To evaluate changes in primary and secondary outcome measures assessed by validated scales at baseline, 6-weeks, and 12-weeks, we will compare within-group differences for each time-point using a t-test if normally distributed, or the Mann Whitney-U test for non-normally distributed continuous data. In addition, effect sizes for the changes within both groups (questionnaire data) and app group (objective sleep parameters) will be computed.

9.9 Quality control

Quality control is defined as the operational techniques and activities, such as monitoring, undertaken within the quality assurance system to verify that the requirements for quality of the study related activities have been fulfilled. Quality control should be applied to each stage of data handling to ensure that all data are reliable and have been processed correctly. Quality assurance is defined as the planned and systematic actions that are established to ensure that the study is performed, and the data generated, documented (recorded) and reported, in compliance with Good Clinical Practice (GCP) and the applicable regulatory requirements.

9.9.1 Access to Source Data/Document

The investigator will permit, and participating subjects will consent for, potential study-related monitoring, audits, Ethics Committee review and regulatory inspections, providing direct access to primary participant's data (i.e. source data) that support data in the Microsoft Azure cloud. Direct access is defined as the permission to examine, analyze, verify and reproduce any records and reports that are important to evaluation of a study. Any party (e.g. domestic and foreign regulatory authorities, the sponsor and/or authorized representatives of the sponsor such as monitors and auditors) with direct access should take all reasonable precautions within the constraints of the applicable regulatory requirements to maintain the confidentiality of users identities and sponsor proprietary information.

9.9.2 Quality assurance:

Quality assurance is defined as the planned and systematic actions that are established to ensure that the study is performed, and the data are generated, documented (recorded) and reported in compliance with GCP and the applicable regulatory requirements.

9.10 Study monitoring

The sponsor or authorized, qualified representatives of the sponsor will accomplish the monitoring during the study. Source documents will be reviewed for verification of consistency. The investigator agrees that representatives or the designees of the sponsor, and appropriate regulatory bodies will be given direct access to the regular files of the user. It is important that the investigator and their relevant personnel are available during the monitoring visits and possible audits and that an appropriate location and sufficient amount of time is devoted to the process. During the monitoring visit a PC with internet connection should be available to the monitor for direct connection to the internet database of the study and to all the data of the users if stored in the data system.

9.10.1 Audit

An audit is a systematic and independent review of study related activities and documents to determine whether the validated study related activities were conducted and the data were recorded, analyzed and accurately reported according to the protocol, designated Standard Operating Procedure (SOPs), GCP and the applicable regulatory requirements.

9.11 Limitations of the research methods

It is expected that variations in the use of the Dein Schlaf. Dein Tag will occur, i.e., some users will use the app very intensely, others might use it regularly but not so intense. Due to the expected of variations in procedures and in particular in usage times of the sleep advice engine, the magnitude of statistical significance (i.e., effect size) is expected to be smaller but still within the range of 0.20 to 0.50.

9.12 Other aspects

None

10. Protection of human subjects

All sleep advice engine support activities used are decided individually by the user and are not pre-defined by the study protocol. All sleep advice engine support activities are to be used in line with their marketing authorisation. Participation does not pose additional risks and adverse events are not expected given the behavioural nature of the intervention. All Sleep advice engine support activities are performed in accordance with all applicable ethical and regulatory standards. Before initiating the study in a country, approval of the IRB / IEC will be obtained.

11. Management and reporting of Adverse Events/Adverse Reactions

Unanticipated problems or any unexpected adverse events will be promptly reported by the PI to an IRB representative from the Ethik-Kommission der Medizinischen Fakultät der Universität Duisburg-Essen by phone ([name]) or email ([contact]), as well as any other medium (e.g. faxed form) requested by the 3rd party IRB following email/phone notification.

12. Plans for disseminating and communicating study results

Study results will be pooled for the purpose of publication that will be jointly coordinated by SleepScore Labs and ResMed. Preparation of the comprehensive publication will occur at the completion of the study. Publications arising from this study will be jointly defined, executed, and published or alternately consented by both sides.

Annex 1. Questionnaires

	Items	Recruitment	Baseline	6 Weeks	12 Weeks	Purpose
Regensburg Insomnia Scale	10	X				Eligibility
SF-B	29		X	X	X	Effect on sleep
SF-12	12		X	X	X	Effect on preventative health
Pittsburgh Sleep Quality Index (PSQI)	19		X	X	X	Effect on sleep quality
Perceived Stress Scale	10		X	X	X	Effect on Stress

2 Responsibility of the statistical analysis of study data

The sponsor ResMed Germany Inc will be responsible for performing analyses on all self-reported sleep and quality of life (questionnaire) data, and Sleepscore Labs Limited will be responsible for the analyses of objectively measured sleep data (application). Both parties will be responsible for the review of each other's data. A detailed description of tasks, responsibilities and timelines is outlined in appendix II.

3 Background

Prevention programs can help to avoid sleep problems and train people who are not satisfied with their sleep how they can sleep better can help to improve quality of life and sleep. The Dein Schlaf. Dein Tag. validation study follows 600 healthy participants, who are either randomized to the app condition or to the waitlist condition, with self-reported sleep problems over a period of 12 weeks to investigate whether the use of a smartphone application can improve subjective sleep behavior and objective sleep quality.

3.1 Objectives and aims

Primary outcome

- Changes in score of the sleep quality (SQ) component of the SF-B comparing app and waitlist condition at baseline with data at 6 and 12 weeks of follow-up.

Secondary outcomes

Changes in subjective sleep parameters (questionnaires) comparing app and waitlist condition at baseline with data at 6 and 12 weeks of follow-up.

- Changes in scores of the “feeling refreshed after sleep” (GES) component of the SF-B
- Changes in physiological and psychological component scores of the SF-12
- Changes in quality of sleep (QoS), measured by the Pittsburgh Sleep Quality Index (PSQI) total score
- Changes in scores of the perceived stress scale (PSS)

Changes in objective sleep parameters in the app condition at baseline with data at 6 and 12 weeks of follow-up.

- Changes in sleep onset latency
- Changes in wake after sleep onset time
- Changes in total sleep time
- Changes in sleep efficiency
- Changes in sleep staging
- Changes in nighttime awakenings

3.2 Design

Decentral prospective interventional randomized study. Sleepy, otherwise healthy participants will be randomized to download and use the application (app condition) or to a waitlist (control condition). Both groups will fill out questionnaires online on their sleep behavior and quality of life status. In the app condition, objective sleep parameters will be documented.

4 Population for analyses

4.1 Definitions

“App condition”: Participants randomized to tracking their sleep with the Dein Schlaf. Dein Tag. application.
“Waitlist condition” (control condition): Participants randomized to a waitlist group without using the application.

4.2 Changes to the protocol

Changes from version May 27 2022 to Jan 26 2023 were that informed consent was given electronically (no personal signature). The flowchart was adapted to show that after participants consented, the baseline assessment was performed and then the randomization. The Munich Chronotype questionnaire and the LISST questionnaire were not provided. Changes from version Jan 26 2023 to Apr 28 2023 were that inclusion criteria were changed to allow recruitment of non-iOS users. Decision on the version Apr 28 2023 was pending until this point in time.

4.3 Violations of the protocol

Participants in the app condition who do not track their sleep for 3 nights or more per week will be excluded from parts of the secondary analyses.

5 Variables

5.1 Demographics and baseline characteristics

The following table lists the variables to characterize demographics and baseline characteristics:

Variable name and unit	Unit
Demographics and inclusion	
Age [yrs]	years
Sex [male/female]	
Weight [kg]	kg
Height [cm]	cm
Objective sleep data and sleep documentation	
sleep onset latency	min
wake after sleep onset time	min
total sleep time	min
sleep staging	min
nighttime awakenings	number

5.2 Primary variable

Score of subjective sleep quality (SQ) component of the SF-B in the app group and waitlist condition after 6 weeks and 12 weeks. SF-B SQ component contains scores of ESS (2 questions), DSS (2 questions), VZA (1 question), ASC (6 questions) and 1 question (28), which are summarized to an SQ score. Results are ranging from 1 (poor sleep quality) to 5 (best sleep quality). Scoring and interpretation will be done following the SF-B manual (revised version) © Hogrefe Verlag 2011.

5.3 Secondary variables

- Score of SF-B GES component: Feeling of being refreshed after sleep. Scoring and interpretation will be done following the SF-B manual (revised version) © Hogrefe Verlag 2011.
- Scores of physiological and psychological component of the sleep questionnaire SF-12. Scoring and interpretation will be done following the SF-12 manual (2nd version) © Hogrefe Verlag 2011.
- Score of the perceived stress scale (PSS). PSS consists of 10 questions, divided into a perceived helplessness subscale PH and a =perceived self-efficacy PSE subscale. The range of answers are: 1 =

never, 2 = almost never, 3 = sometimes, 4 = fairly often, 5 = very often. The subscale PH is calculated by summing up Items 1, 2, 3, 6, 9 and 10. The subscale PSE is calculated by summing up items 4, 5, 7 and 8. A total score can be derived by taking the sum of all PH and reversed PSE items. The items 4, 5, 7 and 8 are reverse scored for the total score. High scores indicate a high level of stress. (Annex III).

- Scores of the Pittsburgh Sleep Quality Index (PSQI). PSQI contains 19 questions (+5 that are not included in the scoring – question 10 does not count for quantitative evaluation) – divided into 7 components - that are rated from 0=very good to 3=very bad. The 7 component scores will be added up to a global score ranging from 0 to 21. PSQI scores will be evaluated according to the scoring manual (Annex IV; in case a version has been updated, the update will be used).
 - sleep onset latency in minutes
 - wake after sleep onset in minutes
 - total sleep time in minutes
 - sleep efficiency in %
 - sleep staging in minutes/stage
 - numbers of nighttime awakenings
 - time spent on guide (average time and/or number of interactions over the duration of the study)

5.4 Dduced, grouped and summarized variables

Sleep efficiency (%) = Total sleep time/time in bed

Body mass index BMI = weight (kg)/height² (m)

6 Treatment of missing values and outliers

6.1 Missing values

Missing values will not be replaced. All available data will be used for analyses. For further details see sections 7 and 8 on statistical methods and analyses.

6.2 Outliers

The analyses comprise all measured and documented values. Excluded are only those values that have been identified or confirmed by an investigator to be a measurement error or a confirmed false entry, e.g. typos in the date of birth.

7 Statistical methods

Demographic and other key study variables will be compared between intervention group and control group at the baseline using t tests for continuous variables and chi squared for categorical variables to test whether the randomization has worked adequately.

The questionnaire data will be analyzed by an ANOVA, with one factor (app condition vs. waitlist control group) and time (Baseline, 6-weeks, 12-weeks). To handle missing values, a mixed-model approach with the same factors will be applied. The critical statistical test would be the interaction term between app condition and the waitlist control group.

For objectively recorded sleep data, repeated measured data will be analyzed using multi-level modeling (MLM) in a nested way (nights within participants), will be performed allowing for analyzing changes with the intervention (app) group. To evaluate changes in primary and secondary outcome measures assessed by validated scales at baseline, 6-weeks, and 12-weeks, we will compare within-group differences for each time-point using a t-test if normally distributed, or the Mann Whitney-U test for non-normally distributed continuous data. In addition, effect sizes for the changes within both groups (questionnaire data) and app group (objective sleep parameters) will be computed.

8 Statistical analyses

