	
critical statistical test would be the interaction term between app condition and the waiting-list control group.
 
Objectively measured data will be analyzed using multi-level modeling (MLM) in a nested way (nights within participants), allowing for analyzing changes within the intervention (app) group. To evaluate changes in primary and secondary outcome measures assessed by validated scales at baseline, 6-weeks, and 12-weeks, we will compare within-group differences for each time-point using a t-test if normally distributed, or the Mann Whitney-U test for non-normally distributed continuous data. In addition, effect sizes for the changes within both groups (questionnaire data) and app group (objective sleep parameters) will be computed.

--	---

4. Amendments and updates

Amendment No. 1, Jan 26 2023

Amendment No. 2, Apr 28 2023

Section	Amendment or update detail	Reason
5 Milestones	Dates changed	Adapted according to preparation of study
9.4 Design	Deleted “written”, added “A participant information document with consent form will be provided with page-turning function. Participant has to agree that his/her data will be used in this study by clicking “yes, I agree” or “no I don’t agree and do not want to participate”.”	Electronic consent ensures that participants can follow a defined workflow and pathway and will be guided smoothly through the recruitment portal. This avoids that too many potential participants are being lost during the course of recruitment.
9.4.1	Adapted flowchart: Informed Consent – then baseline assessment – then randomization	Now follows the routine in study practice. Before the randomization should have occurred before the baseline assessment. Since randomization means access to the app for the “app group”, the timepoint of filling out the baseline questionnaire could have been after first app usage. This will be avoided when doing baseline before randomization and app download.
9.5.1 Data	Deleted Munich Chronotype Questionnaire	Conversion into electronic format problematic; would have compromised the outcomes

9.5.1 Data	Deleted Landecker Inventar zur Erfassung von Schlafstörungen (LISST)	Study flow and assessment of participants for eligibility in the e-portal required a combination of in-/exclusion criteria with the LISST to ensure all screening criteria could be met. LISST is not required to be applied as a separate questionnaire.

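### The primary SF-B sleep quality analysis should hold the arms equal at the pre-randomisation baseline, name its covariance structure, and say what follows the two-visit test

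*SAP*

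**What the plan says.** SAP section 7 and protocol 9.8 plan an ANOVA of the questionnaire data with group and, in the SAP's words, "time (Baseline, 6-weeks, 12-weeks). To handle missing values, a mixed-model approach with the same factors will be applied". Baseline is therefore an outcome level with its own mean in each arm. No covariance structure, sphericity correction, baseline covariate or baseline constraint is given.

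The decisive test is described as "The critical statistical test would be the interaction term between app condition and the waitlist control group". Protocol 9.8 repeats this, and the protocol abstract has nearly the same words: "critical statistical test would be the interaction term between app condition and the waiting-list control group".

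SAP 8.1 looks for a significant difference in SF-B sleep quality between conditions at week 0, week 6 and week 12, and does not say which result decides success. SAP section 7, protocol 9.8 and the abstract also plan within-group tests of the primary outcome at each time-point.

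SAP 4.2 describes the flow after consent: "the baseline assessment was performed and then the randomization". Protocol 9.2 specifies simple 1:1 randomisation. On the analysis set, protocol 9.8 says: "The primary analysis will include all randomized participants". On missing data, SAP 6.1 says: "Missing values will not be replaced. All available data will be used for analyses".

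**The concern.** Three things are unsettled in the analysis that decides the trial.

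- **Baseline.** When baseline precedes randomisation, the arms have the same expected mean at week 0. The planned model still estimates a baseline difference, and the noise in that estimate enters both follow-up contrasts.
- **Error rate.** A three-visit repeated-measures ANOVA holds its nominal level only under sphericity or with a correction. A mixed model needs an adequate covariance structure. Neither is stated.
- **Decision rule.** Two levels of one factor cannot interact. Read as group-by-time, the test has 2 df and no direction, and it does not show which visit differs. Nothing says how a 6-week or 12-week claim follows from it. Baseline, where no treatment effect can exist, is listed as a comparison point, and the within-group tests stand beside the between-arm test without a stated rank.

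At stake are power that could be recovered from data already collected, and control of error for any visit-specific claim.

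**Working it through.** **The plan's own figure.** Protocol 9.6 gives 150 per group for 80% power "assuming an effect size of 0.20", raised to 300 for dropout. Read as a two-sided two-sample comparison of 0.20 SD, the requirement is about 393 per arm, and power at 150 is 0.41. The 150 is not reproduced. That is a separate matter; it is noted here because spare power cannot be taken for granted.

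**Inputs.** From the protocol: 300 per arm, effect 0.20, alpha 0.05. Assumed, because the documents are silent: two-sided testing; effect in follow-up SD units; follow-up SD 1; baseline SD k; one common correlation r between visits (compound symmetry); complete data; 0.20 at both visits unless stated.

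**Precision.** Let s0² be the baseline variance and b the vector of regression slopes of the week-6 and week-12 scores on baseline. For the two arm differences,

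V_free = V_constrained + (2/n)·s0²·(1−b)(1−b)′.

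The added term is never negative, so the constrained 2-df test has at least the noncentrality of the free one.

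**Noncentrality.** With (n/2)·0.20² = 150 × 0.04 = 6,

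- λ_free = 12/(1 + r + 2k² − 4rk)
- λ_constrained = 12/(1 + r − 2r²)

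The denominators differ by 2(k − r)². The gain vanishes when k = r, that is, when the slope r/k equals 1.

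Example, r = 0.5 and k = 1: λ_free = 12/1.5 = 8; λ_constrained = 12/1 = 12. Matching the constrained test with the planned one would take 300 × 12/8 = 450 per arm. Power is taken from the noncentral chi-square on 2 df.

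| Baseline SD ÷ follow-up SD (k) | r | Power, free baseline | Power, constrained |
|---|---|---|---|
| 1.0 | 0.3 | 0.56 | 0.84 |
| 1.0 | 0.5 | 0.72 | 0.88 |
| 1.0 | 0.8 | 0.985 | 0.994 |
| 0.8 | 0.3 | 0.68 | 0.84 |
| 0.8 | 0.5 | 0.82 | 0.88 |
| 0.8 | 0.7 | 0.959 | 0.964 |
| 0.7 | 0.5 | 0.86 | 0.88 |
| 0.7 | 0.7 | 0.964 | 0.964 |

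**Effect at one visit only** (r = 0.5, k = 1): λ goes from 8 to 9 and power from 0.72 to 0.77.

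**Dropout.** Protocol 9.6 says: "As trials with solely online recruitment may have higher drop out rates". It gives no rate. In a simulation with assumed baseline-dependent dropout (waitlist/app missing 26%/32% at week 6 and 37%/42% at week 12; k = 1), power went from 0.47 to 0.68 (r = 0.3), 0.59 to 0.72 (r = 0.5) and 0.93 to 0.95 (r = 0.8).

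**Error rate.** Uncorrected repeated-measures ANOVA, 300 per arm, 20,000 simulated trials with no effect:

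- compound symmetry: 0.051
- AR(1) with correlation 0.7: 0.057
- follow-ups correlated 0.8 with each other and 0.4 with baseline: 0.063

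With an unstructured covariance, in the dropout simulation, the free test rejected 5.0% to 5.1% and the constrained test 4.9% to 5.4%.

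**Visit rule.** Testing each visit at 0.05 only after a significant 2-df test is a closed procedure for two hypotheses. Simulated false visit claims were 3.9% to 4.6% with no effect anywhere. With an effect at one visit only, false claims at the other were 4.7% to 5.0%.

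**The case against.** Group-by-time with baseline as a level is conventional, and the misworded sentence has only one sensible reading, so correcting it is editorial. The power gain is a matter of efficiency, and its size is unknown: the documents give neither SDs nor correlations. Entry is restricted to Regensburg Insomnia Scale scores of 13 to 24, which may narrow the baseline spread and shrink the gain, possibly to nothing. The constraint also depends on an order of events that is not fully settled: SAP 4.2 ties it to the Jan 26 2023 version, while protocol section 5 gives January 2023 as the actual start of enrolment.

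All of that stands as a limit on size and certainty. It does not remove the point: the gain cannot be negative in large samples, the covariance structure is unstated, and the visit rule is missing.

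Stronger readings that the documents do not support:

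- *The planned test is invalid.* The plan does not rule out an unstructured covariance or a sphericity correction. It names neither, so the test cannot be called valid as written either.
- *The trial forfeits a large amount of power.* That needs a low correlation, similar SDs and a sustained effect, all of them assumptions.
- *The constraint repairs the sample size.* At 150 per arm with r = 0.5 and k = 1, power goes only from 0.42 to 0.58.
- *Some participants were randomised before baseline.* The dates leave this possible but do not show it.

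**Conclusion.** The point holds in a limited form. The planned group-by-time test holds 5% only with an unstructured covariance or a sphericity correction, and the plan states neither; the excess in the non-spherical examples is about one percentage point. Constraining the arms equal at week 0 never lowers the large-sample power of the same test. The gain ranges from large (0.56 to 0.84 at r = 0.3 with equal SDs) to none (slope of follow-up on baseline equal to 1), and is modest for a one-visit effect. Those figures rest on an assumed effect pattern, common correlation and SD ratio, so confidence is high in the direction and low in the size. The visit rule is a real but secondary gap. The change should be made before analysis; it is not a fatal defect.

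**What to change.** Replace the primary-analysis text in SAP section 7, protocol 9.8 and the abstract along these lines:

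> Primary model: mixed model on all randomised participants, with SF-B SQ at weeks 0, 6 and 12 as outcomes, unstructured covariance, and arm means constrained equal at week 0 (visit effects, plus group effects at weeks 6 and 12 only). The critical test is the 2-df test of the app-minus-waitlist differences at weeks 6 and 12, at 0.05. Only if it is significant is each visit's difference tested at two-sided 0.05, with direction judged from the estimate.

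Also:

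- Change the interaction sentence to group-by-time in all three places.
- Drop baseline as a comparison point in SAP 8.1.
- Label the within-group tests of the primary outcome as descriptive in SAP section 7, protocol 9.8 and the abstract.
- Confirm from date stamps that every baseline preceded randomisation. For any participant where it did not, do not rely on the constraint: set that baseline value to missing, or make the unconstrained test primary.

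Using baseline as a covariate is nearly equivalent but omits participants with no follow-up value, so the constrained form fits an analysis of everyone randomised better.

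The cost is wording and a date check. No participants, data or alpha are added, and the missing-at-random assumption is the one the planned mixed model already makes.
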